10.6.7 Antibody Formation

The incidence and percentage of subjects who develop anti-evolocumab antibodies (binding and if positive, neutralizing) at anytime will be tabulated.

10.6.8 Exposure to Investigational Product

Descriptive statistics will be produced to describe the patient-month exposure to investigational product and the categorical representation of dose received. Exposure definitions are provided in [Section 6.3](#).

10.6.9 Exposure to Concomitant Medication

The number and proportion of subjects receiving the lipid regulating medications of interest (MOI) will be summarized by category and preferred term for each treatment group as coded by the World Health Organization Drug (WHODRUG) dictionary.

10.7 Pharmacokinetic Analyses

Individual and mean serum evolocumab and [REDACTED] concentration-time profiles will be provided nominal times. The data set will be analyzed and stored in the Pharsight Knowledgebase Server (PKS) data repository using the current version of Phoenix WinNonlin.Evolocumab or [REDACTED] serum concentrations with values below the lower limit of quantification will be reported as less than their respective values but will be set to zero for analysis. PK parameters following the last dose will include but not limited to the maximum and minimum evolocumab serum concentrations observed at the collected timepoints. Individual and summary statistics for PK concentrations will be provided.

These analyses will be performed by the PKDM group.

Compartmental exposure-response analyses will not be specified in this analysis plan but may be included in a subsequent population PK analysis using a single study or as part of a metadata analysis.

11. Changes From Protocol-specified Analyses

As per the memo dated 11th March 2019, Disease-Related Events (DREs) will be removed from protocols and no longer need to be collected by Investigators.

The 20120123 protocol is not being amended to reflect this change since it is an ongoing study close to primary analysis. However, the SAP has been modified to remove all DRE language. DREs will not be reported separately (as specified in the protocol) but will be included as AEs.

12. Literature Citations / References

Hochberg Y. A sharper Bonferroni procedure for multiple tests of significance. *Biometrika* 1988;75:800-802.

Littell, R.M., Pendergast, J and Natarajan, R. Tutorial in Biostatistics. Modelling covariance structure in the analysis of repeated measures data. *Stat Med.* 2000;19: 1793-1819.

Wilson PWF et al. Prediction of Coronary Heart Disease Using Risk Factor Categories. *Circulation.* 1998; 97:1837-1847

Ji C et al. Waist Circumference Distribution of Chinese School-age Children and Adolescents. *Biomedical and Environmental Sciences.* 2010; 23 (1): 12-20.

Rubin DB. (2004) *Multiple Imputation for Nonresponse in Surveys.* 2nd edition. New York: Wiley & Sons.

13. Appendices

Appendix A. Analytical Study Week Assignments

Selected endpoints will be summarized by scheduled study visits in descriptive analyses. Since the actual visits may not exactly coincide with their scheduled visit day, the actual visit day is mapped to the study visit generally by non-overlapping consecutive intervals covering the entire time continuum. The mapping intervals for all distinct schedules are summarized in the following table:

Analytical Study week	Week 4	Week 8	Week 12	Week 16	Week 20	Week 22	Week 24
Scheduled Visit day	29	57	85	113	141	155	169
Vital Signs(sitting BP, HR)	(1,56]		(56,112]		(112,147]	(147,161]	(161,175]
Physical exam(including neurologic examination)							(1,175]
Body weight, waist circumference, Tanner staging, Body height							(1,175]
cIMT							(29,196]
Cogstate neurocognitive assessment							(1,175]
12 lead ECG			(1,126]				(126,175]
Fasting Lipids			(1,119]			(119,161]	(161,175]
Lp(a), ApoA1, ApoB			(1,119]			(119,161]	(161,175]
PK, █████			(1,119]			(119,161]	(161,175]
Chemistry, including fasting glucose			(1,126]				(126,175]
Hematology			(1,126]				(126,175]
Estradiol (females) / testosterone (males)							(1,175]
HbA1c, hsCRP, CK, FSH, LH, ACTH, DHEA-S, cortisol							(1,175]
Anti-evolocumab antibodies			(1,126]				(126,175]
HCV viral load							(1,175]
Urinalysis, urine microalbumin			(1,126]				(126,175]

Handling multiple records assigned to an analytical study week:

If there is more than one record in a study week interval, the analytical record for that specific study week will be defined as the record closest to the scheduled visit day of that specific study week ($7 \times \text{study week} + 1$). If two records are equidistant from the scheduled day, then the earlier record will be chosen. If there are multiple records on the same day, the last record will be used.

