6.3 Other Protocol-required Therapies

All lipid-lowering drugs that are allowed per protocol and that the subject may be taking, must be commercially available and are not provided or reimbursed by Amgen (except if required by local regulation). The investigator will be responsible for obtaining supplies of these drugs. All such therapy needs to be stable and unchanged during the entire time of screening and study participation unless a change is clinically necessary.

6.4 Withholding of Amgen Investigational Product or Statin Background Therapy due to Elevation of Creatine Kinase (CK)

If CK is > 5x ULN, CK must be retested before IP is administered. In addition, investigators will ask study subjects to promptly report muscle pain, cramps, or weakness especially if accompanied by malaise or fever. If such symptoms occur, the subject's CK levels should be measured and if CK is > 5x ULN, the subject should be instructed to discontinue statin background therapy and IP. CK must be retested before any statin or IP is administered.

The following rules apply:

CK at prior visit	CK on retest	Amgen Investigational Product and Non-Amgen Statin Background Therapy Administration
> 5x ULN	> 10x ULN	Discontinue statin and IP ^a . Contact Amgen Medical Monitor
	> 5x to ≤ 10x ULN	Discontinue statin and retest CK before statin administration. Consider continuing IP if alternative explanation
	≤ 5x ULN	Consider continuing IP and statin

^a CK elevations >10x ULN that have been confirmed to be secondary to myocardial infarction do not require discontinuation of Amgen IP or non-Amgen statin background therapy.

If muscular symptoms are severe and cause daily discomfort, even if the CK levels are elevated to ≤ 5x ULN, in consultation with the Amgen medical monitor, discontinuation of statin, or introduction of an alternative statin may be considered at the lowest dose and with close monitoring.

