14. APPENDICES

Appendix A. Additional Safety Assessment Information

Adverse Event Grading Scale

Refer to the NCI Common Terminology Criteria for Adverse Events (CTCAE) Version 4.0 for adverse event grading and information. The CTCAE is available at the following link: http://ctep.cancer.gov/protocolDevelopment/electronic_applications\ctc.htm.

Pediatric Drug-induced Liver Injury Reporting & Additional Assessments

Reporting

Cases with

AST or ALT ≥ 3 x ULN and TBL > 2 x ULN or INR > 1.5

or

AST or ALT ≥ 3 x ULN with signs and symptoms consistent with hepatitis must be reported to Amgen as a serious adverse event within 24 hours of discovery or notification of the event (ie, before additional etiologic investigations have been concluded).

Cases with

AST or ALT > 3 x ULN (if baseline ALT or AST is ≤ 3 x ULN)

AST or ALT > 5 x ULN (if baseline ALT or AST is ≤ 5 x ULN)

are to be reported as adverse events.

The appropriate CRF (eg, Adverse Event CRF) that captures information necessary to facilitate the evaluation of treatment-emergent liver abnormalities is to be completed and sent to the Amgen.

Other events of hepatotoxicity and potential DILI are to be reported as serious adverse events if they meet the criteria for a serious adverse event defined in [Section 9.1.2](#).

Additional Clinical Assessments and Observation

All subjects in whom investigational medicinal product(s) or protocol-required therapies is/are withheld (either permanently or conditionally) due to potential DILI as specified in [Sections 6.5.1](#) and [Section 6.5.2](#) or who experience AST or ALT elevations > 3 x ULN (if baseline ALT or AST is ≤ 3 x ULN) or who experience AST or ALT > 5 x ULN (if baseline

ALT or AST is $\leq 5 \times$ ULN) are to undergo a period of “close observation” until abnormalities return to normal or to the subject’s baseline levels.

The following evaluations are to be performed during this period:

1. Repeat liver tests AST, ALT, ALP, bilirubin (total and direct), and INR as clinically necessary until laboratory abnormalities improve .
2. Obtain pediatric gastroenterologist or pediatric hepatologist consult.

The diagnostic approach (including blood tests) to investigate alternative causes for abnormal liver tests is to be determined in consultation with a pediatric gastroenterologist or hepatologist.

The “close observation” is to continue until all laboratory abnormalities return to baseline or normalize and subject’s clinical condition improves.

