6.3 Other Study Related Definitions

Analytical Study Week Assignments

Analytical windows will be used to assign parameter measurements to study weeks. The algorithm is provided in [Appendix A](#).

Actual Treatment Group

A subject's actual treatment group is the randomized treatment group, unless the subject receives treatment throughout the study that is different than the randomized treatment group assignment, in which case the actual treatment group is the treatment received.

Investigational Product (IP)

Evolocumab SC 420 mg QM and placebo SC QM.

Study Exposure Period in Months

For each randomized subject, Study Exposure Period = (EOS date – Enrollment Date + 1) / 365.25 * 12

IP Exposure Period in Months

IP Exposure Period = [min (Last IP Dose Date + 28 days, EOS Date) - Study Day 1 + 1] / 365.25 * 12

Treatment-emergent adverse event

Treatment emergent adverse events are events categorized as Adverse Events (AEs) starting on or after first dose of investigational product as determined by “Did event start before first dose of investigational product” equal to No or missing on the Events eCRF and up to and including 30 days after last dose of investigational product or the EOS date, whichever is earlier. Any AE that cannot be defined clearly as a TEAE will be considered a TEAE in the database.

Reflexive Approach for LDL-C and VLDL-C

For all analyses related to LDL-C and VLDL-C, unless specified otherwise, an LDL-C reflexive approach will be used. When calculated LDL-C is less than 40 mg/dL or triglycerides > 400 mg/dL, the UC LDL-C **value from** the same blood sample will be used instead of calculated LDL-C and the UC VLDL-C **value from the same blood sample will be used instead of calculated VLDL-C**, if available.

7. Analysis Subsets

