10.6.2 Laboratory Test Results

Descriptive statistics will be provided for actual values and changes from baseline in select laboratory parameters at each protocol-specified scheduled visit. Laboratory analytes are provided in the protocol Table 2. Lab shift tables using the CTCAE v4.03 or later grading will be used for analytes of interest, when applicable. The results will be based on the maximum (ie, worst) shift from baseline to the EOS. In addition, CK and liver function test (LFT) abnormalities will be assessed by the incidence overall and by visits of the following categories:

- CK > 5 x ULN
- CK > 10 x ULN
- ALT or AST \geq 3 x ULN
- ALT or AST \geq 5 x ULN
- Total bilirubin \geq 2 x ULN
- (ALT or AST \geq 3 x ULN) and Total bilirubin \geq 2 x ULN and Alkaline Phosphatase <2 x ULN

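### By-visit CK and liver threshold counts use the record nearest the scheduled day, so unscheduled peaks can go uncounted in those cells

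*SAP*

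**What the plan says.** SAP 10.6.2: "CK and liver function test (LFT) abnormalities will be assessed by the incidence overall and by visits of the following categories". The categories are CK above 5x and 10x ULN, ALT or AST at or above 3x and 5x ULN, total bilirubin at or above 2x ULN, and one combined hepatic category.

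SAP 6.3: "Analytical windows will be used to assign parameter measurements to study weeks". It refers to Appendix A and makes no exception for threshold tables.

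When several records fall in one window, SAP Appendix A keeps a single one: "the analytical record for that specific study week will be defined as the record closest to the scheduled visit day". Ties: "If two records are equidistant from the scheduled day, then the earlier record will be chosen". Same day: "If there are multiple records on the same day, the last record will be used".

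The Appendix A row headed "Chemistry, including fasting glucose" has two windows, (1,126] for Week 12 and (126,175] for Week 24. CK is in the chemistry panel (Protocol Table 2), but Appendix A also names CK in the row with HbA1c, hsCRP and the hormones. That row has one window only, Week 24, (1,175].

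The protocol generates extra samples because a value is high or a symptom occurs. Protocol 6.4 requires CK to be measured when muscle symptoms are reported, and adds: "If CK is > 5x ULN, CK must be retested before IP is administered". Protocol Appendix A, for subjects under close observation: "Repeat liver tests AST, ALT, ALP, bilirubin (total and direct), and INR as clinically necessary until laboratory abnormalities improve".

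**The concern.** A closest-to-target rule is sensible for a mean at a visit, because it keeps the timing comparable. It does not suit a count of subjects who crossed a safety threshold, where the question is whether the value occurred at all. Here the extra records in a window are not a random sample: muscle symptoms or an abnormal result prompt them. An unscheduled peak that loses its place to a normal scheduled draw is exactly the kind of value the table is meant to show.

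At stake is the by-visit half of the multiples-of-ULN tables for CK, transaminases and bilirubin in statin-treated children. If the overall half uses all results, the two halves can also disagree with no explanation in the SAP.

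**Working it through.** **Target days.** Appendix A measures distance from 7 × study week + 1. Week 12: 7 × 12 + 1 = 85. Week 24: 7 × 24 + 1 = 169. Both match its table. Protocol Table 1 gives a visit window of ±3 days, so on-time draws fall on days 82–88 and 166–172.

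**Unscheduled peak, normal scheduled draw.** Let the peak be on day u, the scheduled draw on another day v, and the target be T. The peak is kept only if |u − T| < |v − T|, or if the distances are equal and u is earlier. Since |v − T| ≤ 3, every peak with |u − T| > 3 is dropped. Counting all other days in each window, over the seven possible visit days:

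| Row and window | Other days | Days on which the peak is dropped | Share |
|---|---|---|---|
| Chemistry, Week 12, (1,126] | 124 | 118 to 124 | 95% to 100% |
| Chemistry, Week 24, (126,175] | 48 | 42 to 48 | 88% to 100% |
| Named CK row, Week 24, (1,175] | 173 | 167 to 173 | 97% to 100% |

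These are shares of possible days, not expected event rates. Examples:
- CK 12x ULN on day 40 and 1x on day 85: the Week 12 record is 1x.
- ALT 5x ULN on day 150 and 1x on day 169: the Week 24 record is 1x.

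**Abnormal scheduled draw, later retest.** Let the draw be at offset o = −3 to +3 days from target and the retest k days later. For k ≥ 1 the retest replaces the draw only if |o + k| < |o|. For k = 0 the same-day rule always takes the later record.

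| Days to retest | Offsets at which the abnormal value is lost | Share of 7 offsets |
|---|---|---|
| 0 | all | 7/7 |
| 1 | −3, −2, −1 | 3/7 |
| 2 or 3 | −3, −2 | 2/7 |
| 4 or 5 | −3 | 1/7 |
| 6 or more | none | 0/7 |

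For a retest on a later day, loss therefore needs an early visit and a retest within 5 days. For example, 6x on day 82 and 2x on day 85 keeps 2x, but 6x on day 85 and 2x on day 92 keeps 6x.

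**CK under two rows.** Take CK 12x on day 85, 6x on day 92 and 1x on day 169. Under the chemistry row, Week 12 keeps 12x (distance 0) and Week 24 keeps 1x. Under the named CK row there is no Week 12 cell, and Week 24 keeps 1x: the distances from day 169 are 84, 77 and 0. The SAP does not say which row governs.

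**Size of one lost case.** With the planned 100 and 50 subjects, 1/100 = 1 percentage point on evolocumab and 1/50 = 2 points on placebo.

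**The case against.** The strongest reply is that the overall incidence is a separate summary. Appendix A is written for summaries by scheduled visit, and its rule picks a record for a given study week; an overall incidence has no study week. A reader might infer that peaks vanish from the overall incidence too. The documents do not support that. They are silent on which records feed it, and an event lost by visit may still appear there.

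Nor is Appendix A the SAP's only rule for choosing records. Worst or maximum values are specified for hsCRP (SAP 10.6.1), the CTCAE shift tables (10.6.2) and QTc (10.6.4). But in 10.6.2 the worst-value sentence belongs to the shift tables. The CK and liver categories follow as an addition and carry no such wording, so it cannot be read across to their by-visit counts.

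It is also tempting to say that retesting in general erases high values. The enumeration shows otherwise. Samples go to a central laboratory (Protocol 7.2), so a same-day repeat prompted by the result is unlikely. The CK retest is tied to the next administration of IP; after Week 12 the next scheduled dose is Week 16, 113 − 85 = 28 days later, and a retest at that point never displaces the earlier value.

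Many important peaks are recorded elsewhere. Protocol Appendix A makes ALT or AST above 3x ULN (from a baseline no higher than that) an adverse event, and more severe combinations serious. Protocol 9.2.1 makes laboratory changes that need treatment or a change of therapy adverse events. This cover is real but partial: the shift tables are limited to analytes of interest, and neither they nor the adverse event tables report these ULN multiples by visit.

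Finally, a by-visit table may legitimately show status near the visit. But with a Week 12 window of (1,126], the cell already accepts a value from day 40 when no other record exists. It is not a strict near-visit summary.

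**Conclusion.** The point holds for the by-visit cells only. Applied as written, the one-record rule removes an unscheduled CK, ALT/AST or bilirubin elevation more than 3 days from the target day whenever the scheduled draw was on time. Loss of a retested scheduled value is possible but narrow. For CK the two rows conflict, and under the named row even a scheduled Week 12 elevation is displaced by the Week 24 value.

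The documents do not show that the overall incidence is understated, or that the trial's safety reporting as a whole misses these events. The number of subjects is probably small: the frequency of unscheduled samples is not given, so no expected count can be derived. The working assumes that unscheduled results reach the analysis database; the sevenths read as probabilities only if draws are spread evenly over the visit window. Efficacy analyses and the control of type I error are untouched. The correction is worth making because the affected values are those the table exists to show, and it costs little.

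**What to change.** Amend SAP 10.6.2 and Appendix A to say:

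- For the CK, ALT/AST and bilirubin threshold categories, the by-visit value is the worst of all scheduled and unscheduled results in the window, including same-day repeats.
- The overall incidence uses every post-baseline result to EOS.
- Which Appendix A row, and so which windows, governs CK.
- The closest-record rule stays for descriptive means and changes from baseline.

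The combined hepatic category needs its own line. It requires alkaline phosphatase below 2x ULN, so taking each component's maximum does not define it. Counting a subject when any one sample in the window meets all three conditions would.

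The cost is a few sentences and a small programming change, with no new data. Counts can only stay the same or rise. A peak far from the visit will carry that visit's label (day 40 appears as Week 12), which a footnote can explain.

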Appendix B. Common Terminology Criteria for AEs (CTCAE)

Refer to the NCI Common Terminology Criteria for Adverse Events (CTCAE) for adverse event grading and information. The CTCAE is available at the following link:

<http://evs.nci.nih.gov/ftp1/CTCAE/About.html>

Appendix C. Lipid Modifying Background Therapy

Criteria modified from ACC/AHA guidelines:

	HIGH-INTENSITY STATIN THERAPY	MODERATE-INTENSITY STATIN THERAPY	LOW-INTENSITY STATIN THERAPY	Notes (modifications from ACC/AHA guideline)
Atorvastatin	40 mg or greater QD	10 mg QD up to less than 40 mg QD	Less than 10 mg QD	Atorvastatin 30 mg QD is Moderate intensity.
Rosuvastatin	20 mg or greater QD	5 – < 20 mg QD	less than 5 mg QD	Rosuvastatin < 5 mg QD is low intensity , Rosuvastatin 15 mg QD = moderate
Simvastatin	80 mg or greater QD	20-80 mg QD	< 20 mg QD	And Simvastatin > 40 and < 80 mg QD is moderate, Simvastatin 80 mg or greater QD = high, Simvastatin < 20 mg QD is low-intensity
Pravastatin		40 mg or greater QD	less than 40 mg QD	Pravastatin < 10 mg QD is low intensity
Lovastatin		40 mg or greater QD	less than 40 mg QD	Lovastatin 80 mg QD = moderate, Lovastatin 10 mg QD = Low-intensity
Fluvastatin		80 mg QD	less than 80 mg QD	Fluvastatin 10 mg QD = Low-intensity
Pitavastatin		≥ 2 mg QD	< 2 mg QD	

UNKNOWN-INTENSITY STATIN THERAPY if dose frequency is other or dose unit is other and therefore total daily dose in mg cannot be derived; NO STATIN THERAPY if subject does not use any statin at baseline.
